4.3 Rationale for the Proposed Study

TAK-831 is a highly selective and potent inhibitor of DAO, a peroxisomal enzyme active toward neutral D-amino acids. TAK-831 was shown to increase D-serine levels in the cerebellum of normal rats and it also demonstrated a positive effect on cognition and social interaction in rodent cognition and behavioral models. TAK-831 is under development for the treatment of cerebellar ataxia, and cognitive impairment associated with schizophrenia (CIAS), and negative symptoms

of schizophrenia. The proposed study is aimed at providing evidence of pharmacodynamic (PD) effects of TAK-831 treatment on brain function in subjects with schizophrenia.

A cross-over design was chosen for this study to minimize the potential impact of inter-subject variability on the ability to detect a treatment effect of TAK-831. As each subject serves as his/her own comparator, cross-over designs tend to have greater power to detect treatment effects compared to parallel designs. A placebo control is standard in the evaluation of novel therapeutics for neuropsychiatric disorders; as this study is an add-on to standard therapy in stable subjects the risk of subjects experiencing an exacerbation of their underlying condition is minimized. Preclinical data indicates that PD effects of TAK-831 may be apparent with single doses, supporting the short treatment duration period.

4.4 Benefit/Risk Profile

There is no benefit to subjects in this clinical study.

The following risk mitigation measures will be implemented in this study with TAK-831. These measures are based on what is known about the mechanism of action of TAK-831, nonclinical data, and the 2 phase 1 studies conducted to date, and general considerations in the development of new chemical entities. Procedures may be added during the study if necessary based on evaluation of any additional clinical or nonclinical safety data.

- The dosing and duration of TAK-831 proposed for this study has been used in prior studies in healthy subjects and have not resulted in a safety signal that would prevent additional studies.
- Acute hypersensitivity/anaphylactic reactions to new chemical entities are always a possible risk in any clinical study. Appropriate procedures should be used to manage such possible risks.
- Subjects with a risk of suicide according to the investigator's clinical judgment (or as assessed by the Columbia-Suicide Severity Rating Scale [15]), or who have made a suicide attempt in the previous 12 months, will be excluded from this study. The Columbia-Suicide Severity Rating Scale (C-SSRS) will be administered at prescribed intervals to monitor emergent suicidality. Subjects should be monitored for any signs of suicidal ideation or behaviors, and appropriate psychiatric interventions or other precautions should be instituted, if warranted.
- Emesis and diarrhea were reported in laboratory animals exposed to TAK-831 and in clinical studies in healthy subjects. Nausea has been observed in clinical studies in subjects taking TAK-831, but there has been no consistent relationship observed between frequency or severity of nausea and dose of TAK-831, and all reports of nausea at the highest dose examined in the TAK-831-1005 study were mild in severity. Subjects will be informed of these findings and instructed to contact the investigator for guidance in the management of these symptoms and possible ways to mitigate them.
- Postural hypotension and dizziness were observed in prior studies in healthy subjects.
 However, the incidence of dizziness in subjects treated with TAK-831 and placebo was similar. In addition, some healthy subjects who received TAK-831 met vital signs criteria

consistent with orthostatic hypotension without accompanying clinical symptoms, although a number of these observations were considered not related to TAK-831. Subjects will be informed of these findings and instructed to contact the investigator for guidance in the management of these symptoms and possible ways to mitigate them.

- Eosinophilic intranuclear inclusion bodies (EIIBs) were observed in the proximal tubule epithelium of the kidneys at doses of ≥10 mg/kg/day in rats. The EIIBs were not accompanied by apparent necrosis, inflammation, or impaired renal function and were not considered adverse. Similar findings have been reported in the literature and are considered to be species-specific to the rat [16]. There have been no findings of elevations in creatinine in clinical studies with TAK-831 summarized above; creatinine will continue to be measured in the clinical studies.
- Study procedure—specific risks include issues relating to blood collection for safety assessment/ pharmacokinetic (PK) monitoring (venipuncture may cause bruising), and the placement of electrocardiogram (ECG) pads, which may cause some local redness and/or erythema/itching. The PD assessments planned for the study, aside from those requiring a blood draw, are noninvasive and are associated with minimal risk.

5.0 TRIAL OBJECTIVES AND ENDPOINTS

5.1 Trial Objectives

5.1.1 Trial Primary Objective

 To determine whether TAK-831 is superior to placebo in improving cerebellar function as measured with the average % of conditioned responses during the eyeblink conditioning (EBC) test.

5.1.2 Trial Secondary Objectives

- To determine whether add-on TAK-831 compared to placebo improves sensory processing as measured by ERPs mismatch negativity (MMN) and p300.
- To determine whether add-on TAK-831 compared to placebo improves the auditory steady-state response (ASSR) to 40 Hz stimulation.
- To determine whether add-on TAK-831 compared to placebo improves the composite score of the BACS battery.
- To assess the safety and tolerability of TAK-831.
- To assess the PK of TAK-831.
- To assess the PD of TAK-831 by measurement of plasma D-serine and L-serine levels, as well as plasma D-serine: total serine ratios.

5.2 Endpoints

5.2.1 Primary Endpoints

Average % of conditioned responses during the EBC test at Day 8.

5.2.2 Secondary Endpoints

- MMN amplitude at Fz (electroencephalogram [EEG]) at Day 8.
- P300 amplitude at midline parietal electrode (Pz) (EEG) at Day 8.
- ASSR at midline central electrode (Cz) (EEG) at Day 8.
- BACS cognitive battery composite score at Day 7.
- Plasma D-serine and L-serine levels, and plasma D-serine:total serine ratio at Day 8.
- TAK-831 plasma concentrations.

5.2.4 Safety Endpoints

- Percentage of subjects who experience at least 1 treatment-emergent adverse event (TEAE).
- Percentage of subjects who meet the markedly abnormal criteria for safety laboratory tests at least once postdose.
- Percentage of subjects who meet the markedly abnormal criteria for vital sign measurements at least once postdose.
- Percentage of subjects who meet the markedly abnormal criteria for safety ECG parameters at least once postdose.
- Percentage of subjects with treatment-emergent suicidal ideation or suicidal behavior as measured using the C-SSRS.

6.0 STUDY DESIGN AND DESCRIPTION

6.1 Study Design

This study is a randomized, double-blind, placebo-controlled, 2-period crossover phase 2 study to evaluate the PD effects, safety, tolerability and PK of multiple daily oral doses of TAK-831 in adult patients with schizophrenia.

Approximately 32 adult male and female subjects between ages 18 and 60, inclusive, with a current Diagnostic and Statistical Manual of Mental Disorders, Fifth Edition (DSM-5) diagnosis of schizophrenia who are receiving stable antipsychotic therapy (no increase, no decrease >25% in dose in the preceding 2 months) will be randomized in to the study. Subjects will have a PANSS NSFS of at least 15 with no fluctuation between Screening and Baseline >25%. PANSS total score will not exceed 90 points with no fluctuations between Screening and Baseline >25%. Subjects with extrapyramidal signs or symptoms or depressive symptoms will be excluded.

Additional screening assessments include a physical and neurological exam, clinical laboratory and ECG measures, a urine drug screen, and screening for suicidality and depression using the C-SSRS and the Calgary Depression Scale Score (CDSS), respectively. Assessment of extrapyramidal symptoms will be performed with the Simpson Angus Scale (SAS). The presence of dyskinesias will be assessed with the Abnormal Involuntary Movement Scale (AIMS).

During the pretreatment days (Days -2 and -1), subjects will participate in a baseline assessment with a cognitive battery, PANSS, EEG/ERP measures, and the EBC test.

Effects of up to 2 dose levels of TAK-831 or placebo will be assessed. Each treatment will be administered daily for a period of 8 consecutive days, separated by a 14- to 21-day washout (see Section 2.0 Study Schematic).

The planned dose levels of TAK-831 to be evaluated will be 500 and 50 mg.

The study will consist of 2 treatment periods, and visits to the clinic at the following times: (1) Screening Period (Days -30 to -3) covering full medical, neurological, and psychiatric examinations; (2) Treatment Visits and inpatient stays: On Day -2 of Periods 1 and 2, subjects will be admitted to the clinic for 2-night stays; on Day -2, subjects will undergo baseline clinical assessment procedures and cognitive battery assessment. On Day -1, subjects will receive the baseline EEG and EBC assessments. In Period 1, those who continue to meet all eligibility criteria will be randomized via an interactive response technology (IRT) system to 1 of 2 treatment sequences. On Day 1, subjects will undergo predose blood PK/PD samples, first dosing, and postdose blood draws, after which they will be discharged from the clinic to continue dosing at their residence. Subjects will receive double-blind treatment from Days 1 through 8 (inclusive) with completion of efficacy and PK/PD-related assessments on Days 7 and 8 of each treatment period; and (3), a washout period between Treatment Periods 1 and 2 lasting between 14 to 21 days.

The study schedule is detailed in Table 6.a.

Table 6.a Part 1: Study Schedule

Screening Period	Pretreatment	Dose Administration Period 1 (a)	Washout (b, c)	Dose Administration Period 2 (a)	Follow-Up (c)
Day -30 to -3	Period 1 Days -2, -1, 1	Days 1 to 8	Days 9 to 22	Days 1 to 8	Period 2 Day 20±2

- (a) Subjects will be admitted to the clinic on the afternoon of Day -2 of each period for pretreatment assessments. On Day -2, they will receive clinical assessments and cognitive testing, and on Day -1 they will receive EBC and EEG/ERP assessments. On Day 1, they will receive the first dose of study medication and predose and postdose PK assessments. Study drug for Days 3 to 6 may be dispensed to the participant to take at their place of residence or may be dispensed at the clinic through a qualified member of the research team. On Day 7 in the morning, subjects will be admitted to the clinic for a 1 night stay. On Days 7 and 8, they will receive drug and specified study procedures. (b) Washout duration may range from 14 to 21 days based on emerging data.
- (c) A follow-up safety visit will be performed 10 to 14 days after the last dose in Period 2. Subjects may be brought back to the study clinic for re-evaluation at any time during the study per investigator's discretion.

Study participants will receive daily study drug dosing until Day 8 of each period. Clinical assessments, laboratory tests and ECG will be repeated after dosing on Days 7 and 8 as per the schedule of events. Upon completion of the first dosing period, subjects will enter a washout period lasting between 14 to 21 days and will then return to the study site to undergo Day -2 procedures for the next dosing period.

Approximately 10 to 14 days after the last dose of study drug in the second dosing period, a follow-up safety assessment will be performed.

In the event of a subject prematurely discontinuing the study during one of the study periods, an Early Termination Visit must be conducted, at which the safety, PK, plasma D- and L-serine assessments corresponding to a Final Visit will be performed. If a subject discontinues the study during the washout period, only the procedures corresponding to the follow-up safety assessment will be performed.

Subjects who drop out before completing 2 treatment periods of the study may be replaced at the discretion of the study sponsor.

Subjects who do not meet symptom or medication stability criteria (or other entry criteria that may be met by the subject at a future time) may be considered for rescreening with the approval of the sponsor or designee.

Subjects who have been screened but have exceeded the 28-day Screening Period may proceed in the study after a discussion with the sponsor/designee to obtain approval and to determine whether any screening procedures should be repeated before admission on Day -2 of Period 1.

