3.0 SCHEDULE OF STUDY PROCEDURES

		Periods 1 and 2 (a)							Early				
	Screening	Pretreat- ment Day Treatment Day (c)		Safety Follow-Up (b)	Termina- tion Visit								
Study Day	Days -30 to -3	-2	-1	1	2	3	4	5	6	7	8	Post- Treatment 2 Day 20±2	
Administrative Procedu										,		Day 2012	
Confinement		X	X						T T	X			
Informed consent	X	21	71							21			
Inclusion/exclusion criteria (d)	X	X	X	X									
Demographics/ medical history	X												
Medication history	X												
Concurrent medical	X												
conditions													
Clinical Procedures/Asso	essments												
Full physical examination	X	X								X			X
Psychiatric examination	X												
Height	X												
Weight, and BMI	X												
Vital signs (oral [floor of the mouth]/ tympanic temperature) (e)	X	X	X	X						X	X	X	X
Concomitant	X	X	X	X						X	X	X	X
medications (e)													
ECG	X	X								X			X
C-SSRS	X	X								X		X	X
CDSS	X												
SAS	X												
AIMS PANSS	X	X								X			
EBC test (f)	Λ	Λ	X							Λ	X (f)		
ERPs (f, g)			X								X (f)		
Resting state EEG (f)			X								X (f)		
BACS cognitive battery (f)		X	Λ							X (f)	A (1)		
Dispense study medication (h)				X									
Study drug dosing (c) (h)				X	X	X	X	X	X	X	X		
AE assessment (e)	X	X	X	X				 	T	X	X	X	X
Laboratory Procedures												-	
Clinical laboratory tests (hematology, serum chemistry, urinalysis) (i)	X	X									X		X
Hepatitis panel (HBsAg and Anti-HCV)	X												
FSH	X												
Pregnancy test (hCG) (i) (j)	X	X								X		X	X
Drug screen (i)	X	X								X			X

			Periods 1 and 2 (a)								Early		
		Pret	reat-					Safety	Termina-				
	Screening	men	t Day			T	reatm	ent D	ay (c)			Follow-Up (b)	tion Visit
												Post-	
	Days											Treatment 2	
Study Day	-30 to -3	-2	-1	1	2	3	4	5	6	7	8	Day 20±2	
PK Evaluations													
PK blood collection (m)				X						X	X		X
PD/Biomarker Evaluation	ons												
Blood collection (D- and				X						X	X		X
L-serine) (n)													

AE=adverse event, BMI-body mass index, ERP=event-related field, FSH=follicle-stimulating hormone, HBcAg=hepatitis B core antigen, hCG=human chorionic gonadotropin, HCV=hepatitis C virus, PANSS=Positive and Negative Syndrome Scale.

- (a) A washout interval of 14 to 21 days will separate the last dose of study drug in Period 1 and the first dose in Period 2.
- (b) A follow-up safety visit will be conducted 10 to 14 Days post-treatment Period 2.

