10.2.8 Collection and Reporting of AEs, SAEs, Special Interest AEs, and DILI

10.2.8.1 Collection Period

Collection of AEs (ie, AEs, SAEs, Special Interest AEs, and DILI) will commence at the time the subject signs the informed consent. Routine collection of AEs will continue until the follow-up visit 10 to 14 days after the last dose of investigational product. For subjects who discontinue prior to the administration of study medication, AEs will be followed until the subject discontinues study participation.

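### AE collection runs to a visit 10 to 14 days after the last dose, but no such visit is scheduled for a subject who stops during Period 1 treatment

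*Protocol*

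**What the plan says.** **Collection rule.** Protocol 10.2.8.1: "Routine collection of AEs will continue until the follow-up visit 10 to 14 days after the last dose of investigational product". The one exception is for subjects who were never dosed: "For subjects who discontinue prior to the administration of study medication, AEs will be followed until the subject discontinues study participation".

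**Where the follow-up visit is scheduled.** Protocol 6.1: "Approximately 10 to 14 days after the last dose of study drug in the second dosing period, a follow-up safety assessment will be performed". Note (b) to the schedule in section 3.0 agrees: "A follow-up safety visit will be conducted 10 to 14 Days post-treatment Period 2". Table 6.a, with its note (c), also ties the visit to Period 2, at Day 20±2.

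**What early leavers get.** For a stop on treatment, 6.1 says "In the event of a subject prematurely discontinuing the study during one of the study periods, an Early Termination Visit must be conducted", with safety, PK and serine "assessments corresponding to a Final Visit will be performed". No day relative to the last dose is given, and 7.6 adds no later contact. For a stop between periods, 6.1 says "If a subject discontinues the study during the washout period, only the procedures corresponding to the follow-up safety assessment will be performed".

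**Other provisions.** Section 10.2.8.2 has AEs that have occurred monitored until they settle. Table 6.a note (c) lets the investigator recall a subject. Section 4.4 counts C-SSRS assessments at set intervals among the risk mitigations. SAP 7.11.1 tabulates treatment-emergent AEs with onset up to 30 days after dosing.

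**The concern.** The collection period in 10.2.8.1 is defined by a visit that a Period 1 on-treatment stopper does not have. This subject never receives a Period 2 dose, so a visit placed after Period 2 has no date for them. Section 10.2.8.1 still implies a duty to collect their AEs, but the visit schedule contains no contact through which to do it. A subject who stops in the washout does get the follow-up assessment, and no reason is given for treating the two cases differently.

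At stake is the scheduled detection of new events shortly after exposure, including new suicidal ideation, in subjects some of whom will have left because of an adverse event. An event in the gap would count in the SAP's 30-day tables if it came to light, but nothing is scheduled to find it. Section 10.2.8.3 also applies different SAE reporting rules during and after the collection period, so a site could be unsure which rule applies once the subject has gone.

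**Working it through.** No power or alpha calculation applies. The check sets the visit rules side by side and counts days.

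1. **Reproduce the plan's own window.** The follow-up visit is Period 2 Day 20±2, which is Day 18 to 22. The last dose is on Day 8. 18 - 8 = 10 and 22 - 8 = 14, so the stated 10 to 14 days holds for a Period 2 completer.

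2. **Compare the cases.**

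| Subject | Scheduled safety contact after the last dose |
|---|---|
| Completes Period 2 | Follow-up visit at 10 to 14 days |
| Stops in the washout | Follow-up assessment procedures |
| Stops during Period 2 treatment | Early Termination Visit; the follow-up visit arguably applies too, but 6.1 and 7.6 do not say so |
| Stops during Period 1 treatment | Early Termination Visit only, day not stated |

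3. **Size of the gap.** Let t be the days from last dose to the Early Termination Visit. Shortfall against the 10-day minimum = max(0, 10 - t). The documents do not give t, so these values are assumptions:

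| t (assumed) | Shortfall, days |
|---|---|
| 0 | 10 |
| 3 | 7 |
| 7 | 3 |
| 10 or more | 0 |

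The SAP exempts Early Termination observations from its 3-day limit for summary tables (7.11.2, 7.11.3), so it does not assume that t is 3 or less.

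4. **What is not repeated.** The visible schedule rows give the Early Termination Visit 11 items: physical examination, vital signs, concomitant medications, ECG, C-SSRS, AE assessment, clinical laboratory tests, pregnancy test, drug screen, PK and serine. The follow-up visit has 5: vital signs, concomitant medications, C-SSRS, AE assessment and pregnancy test. All 5 are among the 11, so what is missing is one later repeat of those 5.

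5. **Is the gap inside the reporting window?** SAP 7.11.1 requires onset - last dose + 1 ≤ 30, which allows onset up to 29 days after the last dose. Days t + 1 to 10 lie inside that.

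6. **Comparator for C-SSRS and pregnancy test.** Schedule note (a) says: "A washout interval of 14 to 21 days will separate the last dose of study drug in Period 1 and the first dose". A Period 1 completer is next assessed on Period 2 Day -2, two days before that first dose: 14 - 2 = 12 to 21 - 2 = 19 days after the last Period 1 dose. If the washout is read from 6.1 as ending before Day -2, the figure is about 14 to 21 days. Either way a later assessment is scheduled. For the Period 1 on-treatment stopper none is scheduled after Early Termination.

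**The case against.** The strongest reply is that 10.2.8.1 is the controlling rule. It is tied to the subject's own last dose and exempts only the never-dosed, so the duty already exists and the other sections merely fail to repeat it. The duty does exist. But 6.1, 7.6 and the schedule tell the site which visits to hold, and a site following them would hold none after Early Termination.

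A second reply is that the Early Termination Visit is the exit visit and is the fuller of the two. It is fuller, but a richer assessment at one time does not observe later days. If it closed collection, that would contradict 10.2.8.1 whenever it fell before day 10.

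Third, those most in need are covered elsewhere: known AEs are followed, liver stoppers have repeat laboratory tests under 7.5, recall is possible, and related SAEs reported late still reach the sponsor. This stands and narrows the point to detection of new events. Discretionary recall is not a scheduled contact. Many subjects who withdraw or are lost will not attend in any case, which limits what a fix can recover.

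Fourth, the C-SSRS is prescribed at Early Termination, so the promise in 4.4 is arguably met, and even Period 1 completers wait longer than 10 days for the next one. The 30-day window also outlasts scheduled contact for completers. Both facts are correct. They show that the gap is modest, but those subjects still have a later scheduled contact and this one does not.

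**Conclusion.** The concern holds, at minor severity. For a subject who stops during Period 1 treatment, the visit schedule does not deliver the AE collection period that 10.2.8.1 sets. The shortfall is 0 to 10 days of scheduled detection per affected subject, depending entirely on the unstated timing of the Early Termination Visit; the 10-day end assumes that visit falls on the day of the last dose.

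The documents do not say how many subjects will stop this way, so no share of subjects or total loss is claimed. The safety summaries are descriptive, the primary EBC analysis is not touched, and nothing in the documents shows that stopping will differ between TAK-831 and placebo. The conclusion takes stopping to mean leaving the study, as 6.1 does. For Period 2 on-treatment stoppers the existing wording arguably suffices, and the change needed there is clarification only.

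**What to change.** In 6.1, 7.6, schedule note (b) and Table 6.a note (c), state that any dosed subject who discontinues during either treatment period also has the existing follow-up safety assessment 10 to 14 days after their own last dose. Allow a telephone AE check if the subject will not attend. State that an Early Termination Visit falling in that window serves as both. Section 10.2.8.1 can stay as it is.

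The cost is protocol wording plus one already-defined short visit, or a call, for the subjects affected, some of whom will decline. Vital signs from the visit would fall outside the 3-day limit in SAP 7.11.3, so they would add only to listings and markedly abnormal counts.
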